10.3. List of AESIs with Data Sources and Definitions of SMQ/CMQ

Table 6: Summary of AESIs and the Methods of Data Collections and Derivations

AESI	Using an e-CRF specific tick box on AE page	Using Standard MedDRA Query (SMQ)/company MedDRA Query (CMQ) or lab data
Anaphylactic reactions	Yes	No
General allergic events	No	SMQ “hypersensitivity” (broad and narrow) excluding the following preferred terms linked to local injection site reactions (“infusion site dermatitis”, “infusion site hypersensitivity”, “infusion site rash”, “infusion site urticaria”, “injection site dermatitis”, “injection site hypersensitivity”, “injection site rash”, “injection site urticaria”, “injection site vasculitis”) plus “idiopathic angioedema”
Infusion reactions	Yes	No
Hepatic Disorders	No	
 • SMQ Drug-related hepatic disorder • Potentially clinically significant value (PCSV) in Appendix 10.4, • Hy’s law eDISH plot,
Pregnancy	Yes	No
Symptomatic overdose with investigational medicinal product	Yes	No
Neurocognitive events	No	CMQ for neurocognitive events as define based on Regulatory Agency request for another lipid lowering program (See Table 5 in Appendix 10.3 for the list of terms)
New onset of diabetes (NOD)	No	No medical history of diabetes as specified in “Cardiovascular History and Cardiovascular Risk Factors” CRF page AND one of the following criteria: 
 • Lab criteria: At least 2 values of HbA1c \geq6.5% during the TEAE period. NOTE: For patients with only a single measurement available during the TEAE period,

AESI	Using an e-CRF specific tick box on AE page	Using Standard MedDRA Query (SMQ)/company MedDRA Query (CMQ) or lab data
		
a single value $\geq 6.5\%$ will be considered and qualify the patient as NOD by default. For patients with several HbA1c measurements but only with the last one $\geq 6.5\%$, this single value $\geq 6.5\%$ will be considered and qualify the patient as NOD by default.
 
OR
 
 Lab criteria: At least 2 values of fasting glucose ≥ 126 mg/dL (7.0 mmol/L). NOTE: For patients with only a single measurement available during the TEAE period, a single value ≥ 126 mg/dL (7.0 mmol/L) will NOT be considered and will NOT qualify the patient as NOD. For patients with several fasting glucose measurements but only with the last one ≥ 126 mg/dL (7.0 mmol/L), this single value ≥ 126 mg/dL (7.0 mmol/L) will NOT be considered and will NOT qualify the patient as NOD. 
OR
 
 HLT Diabetes mellitus (incl subtypes) 
OR
 
 Initiation of any new concomitant medication for hyperglycemia during the treatment period
Pancreatitis	Yes	No

Table 7: CMQ “Neurocognitive disorders – FDA’s recommendation”

MedDRA level	MedDRA Term Label
PTCD	Amnesia
PTCD	Amnesic disorder
PTCD	Anterograde Amnesia
PTCD	Behavioural and Psychiatric Symptoms of Dementia
PTCD	Change in sustained attention
LLTCD	Cognitive Deterioration

MedDRA level	MedDRA Term Label
PTCD	Cognitive Disorder
LLTCD	Confusion
LLTCD	Confusion Aggravated
PTCD	Confusional State
PTCD	Delirium
PTCD	Dementia
PTCD	Dementia Alzheimer's type
LLTCD	Dementia Nos
LLTCD	Dementia Nos Aggravated
LLTCD	Dementia of the Alzheimer's type NOS
PTCD	Dementia with Lewy Bodies
PTCD	Disorientation
PTCD	Disturbance in attention
PTCD	Executive dysfunction
PTCD	Frontotemporal Dementia
LLTCD	Global Amnesia
PTCD	Illogical Thinking
PTCD	Impaired reasoning
PTCD	Incoherent
PTCD	Judgement impaired
PTCD	Memory Impairment
PTCD	Mental Impairment
LLTCD	Mental Impairment Nos
LLTCD	Mental State Abnormal Aggravated
PTCD	Mental Status Changes
PTCD	Mini Mental Status Examination Abnormal
PTCD	Presenile Dementia
PTCD	Retrograde Amnesia
PTCD	Senile Dementia
LLTCD	Senile Dementia Nos
LLTCD	Short-term Memory Loss
PTCD	Thinking Abnormal
LLTCD	Thinking Slowed
PTCD	Transient Global Amnesia
PTCD	Vascular Dementia

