10.1.4. Events that Require Expedited Reporting to Sponsor

The following events also require reporting to the sponsor (or designee) within 24 hours of learning of the event:

- SAEs.
- **Adverse Events of Special Interest (AESI; serious and nonserious):** Adverse events of special interest for this study include the following:
 - Anaphylactic reactions

- Allergic reactions that require consultation with another physician for further evaluation or requiring medical treatment
- Moderate or severe infusion reactions
- Increase in ALT or AST: $\geq 3 \times$ ULN (if baseline $<$ ULN), or ≥ 2 times the baseline value (if baseline \geq ULN)
- Symptomatic overdose with investigational medicinal product
- Neurocognitive events
- Pancreatitis
- New onset of diabetes (NOD) in patients without diabetes at baseline. New onset of diabetes is defined as either:
 - At least 2 HbA1c measurements $\geq 6.5\%$ during the TEAE period (NOTE: For patients with only a single measurement available during the TEAE period, a single value $\geq 6.5\%$ will qualify the patient as NOD by default)
 - At least 2 fasting glucose measurements ≥ 126 mg/dL (7.0 mmol/L). For patients with several fasting glucose measurements but with only the last one ≥ 126 mg/dL (7.0 mmol/L), this single value ≥ 126 mg/dL (7.0 mmol/L) will NOT be considered and will NOT qualify the patient as NOD)
 - NOTE: Diabetes at baseline is based on documented medical history, baseline fasting glucose ≥ 126 mg/dL (7.0 mmol/L), or baseline HbA1c $\geq 6.5\%$
- **Pregnancy:** It is the responsibility of the investigator to report to the sponsor (or designee), within 24 hours of identification, any pregnancy occurring in a female or female partner of a male, during the study or within 24 weeks of the last dose of study drug. Any complication of pregnancy affecting a female study patient or female partner of a male study patient, and/or fetus and/or newborn that meets the SAE criteria must be reported as an SAE. Outcome for all pregnancies should be reported to the sponsor.

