4.8.1.2. Adverse Events of Special Interest

Adverse events of special interest (AESI) are AEs (serious or non-serious) required to be monitored, documented, and managed in a pre-specified manner. AESIs will be recorded on the adverse event e-CRF using dedicated tick boxes, and/or identified using standard MedDRA queries (SMQ), company MedDRA queries (CMQ), MedDRA terms, and/or applicable laboratory assessments. [Appendix 10.3](#) contains the definitions used to identify AESIs:

The AESIs include:

- Anaphylactic reactions (e-CRF)
- General allergic events (SMQ)
- Moderate or severe infusion reactions (e-CRF)
- Hepatic Disorder (SMQ, lab data)
- Pregnancy (e-CRF)
- Symptomatic overdose with investigational medicinal product (e-CRF)
- Neurocognitive events (CMQ)
- New onset of diabetes (NOD) (lab data, HLT, and concomitant medications)
- Pancreatitis (e-CRF)

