Individual patient laboratory parameter measurements will be additionally evaluated by PCSV criteria (See Appendix 10.4), specifically identifying patients with at least one post-baseline measurement that meets the PCSV criteria within the respective TEAE periods. These laboratory parameters will be presented by the biological functions defined in Section 4.8.2. The incidence of PCSVs at any time during the respective TEAE periods will be summarized regardless of the baseline level, and again according to the following baseline categories:

- Normal (according to PCSV criterion/criteria)/missing
- Abnormal according to PCSV criterion or criteria

Patient listings of laboratory measurements that meet PCSV criteria will be provided for the report appendix. For those laboratory parameters that don't have an associated PCSV criteria, similar summary tables can be provided based on measurements outside the central laboratory normal ranges, if applicable.

Drug-induced liver injury

For respective treatment period, an evaluation of drug-induced serious hepatotoxicity (eDISH) with the graph of distribution of peak values of ALT versus peak values of total bilirubin will also be presented using post-baseline values during respective TEAE periods. Note that the ALT and total bilirubin values are presented on a logarithmic scale. The graph will be divided into 4 quadrants with a vertical line corresponding to 3 x ULN for ALT and a horizontal line corresponding to 2 x ULN for total bilirubin.

Patient listing of possible Hy's law cases identified (i.e., patients with any elevated ALT > 3 x ULN, and associated with an increase in bilirubin > 2 x ULN, concomitantly or not) with ALT, AST, ALP, total bilirubin, and if available direct and indirect bilirubin will be provided.

Sex hormones

For respective treatment period, the sex hormones will be described separately by gender.

- For girls
 - Values and changes from baseline will be descriptively summarized by time point for estradiol, FSH and LH.
 - Similar table as for PCSA will be provided using normal range during the respective TEAE period. The number (%) of patients with at least one estradiol

value <LLN and LH >ULN, estradiol value<LLN and FSH >ULN, estradiol value <LLN and LH>ULN and FSH >ULN) during the TEAE period.

- For boys
 - Values and changes from baseline will be descriptively summarized by time point for testosterone, FSH and LH.

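### The SAP's derived AESIs do not reproduce the protocol's: Hy's law outputs are triggered by ALT alone, the hepatic AESI has no defined threshold, and a late treated infusion-site allergic event fits no AESI row

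*SAP*

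**What the plan says.** Protocol 10.1.4 sets the AESIs and their urgency: "The following events also require reporting to the sponsor (or designee) within 24 hours of learning of the event". Three of them matter here.

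- Liver: "Increase in ALT or AST", met at 3 x ULN or more if baseline is below ULN, or at twice baseline or more if baseline is at or above ULN.
- Allergy: "Allergic reactions that require consultation with another physician for further evaluation or requiring medical treatment".
- "Neurocognitive events", with no term list.

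Protocol 11.4.5.1 promises a summary of treatment-emergent AESIs.

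SAP 4.8.1.2 is open about sources: "AESIs will be recorded on the adverse event e-CRF using dedicated tick boxes, and/or identified using standard MedDRA queries (SMQ", followed by company queries, MedDRA terms and laboratory data. SAP 5.8.2 builds the AESI tables from Appendix 10.3. There, Table 6 has a column headed "Using an e-CRF specific tick box on AE page", and the entry is no for general allergic events, hepatic disorders and neurocognitive events. Those rows are derived as follows.

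- Hepatic: a drug-related hepatic query, the potentially clinically significant values (PCSVs) of Appendix 10.4, and the Hy's law eDISH plot.
- Allergic: the hypersensitivity query less nine infusion-site or injection-site terms, plus idiopathic angioedema.
- Neurocognitive: "CMQ for neurocognitive events as define based on Regulatory Agency request for another lipid lowering program".

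SAP 5.8.3 lists as possible Hy's law cases "patients with any elevated ALT > 3 x ULN, and associated with an increase in bilirubin > 2 x ULN, concomitantly or not". Its eDISH plot sets peak ALT against peak total bilirubin, and the combined PCSV row in 10.4 pairs ALT with bilirubin. AST is printed in the listing but does not bring a patient into it. SAP 1.2.4 declares no departure from the protocol's statistical section.

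**The concern.** Sites report AESIs by one set of rules and the tables count them by another, with no output that reconciles the two. The study plans 6 patients in Part A and 14 in Part B, so a single patient moved into or out of a row visibly changes the result. The liver outputs matter most. Protocol 8.4.2.1 gives Hy's law as an example of a reason for permanent discontinuation, and the protocol treats ALT and AST as a pair both in exclusion criterion 12 (Section 7.2.2) and in the AESI rule. The outputs meant to find combined enzyme and bilirubin rises use only one of the two enzymes.

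**Working it through.** No sample-size or power figure bears on this point, so there is no plan figure to reproduce. The check applies each document's rule to the same values. All enzyme and bilirubin values are multiples of ULN.

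**Inputs.** Protocol rule (10.1.4): positive if baseline < 1 and value ≥ 3, or if baseline ≥ 1 and value ≥ 2 × baseline. SAP steps (10.4), applied to ALT and AST separately: value > L with baseline ≤ L, for L = 2, 3, 5, 10, 20. SAP Hy's law rule (5.8.3): ALT > 3 and bilirubin > 2. Entry limit (Protocol 7.2.2): ALT and AST not above 3 at screening.

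**1. AST-driven case.** Take AST 4, ALT 2.5 and bilirubin 2.5, assuming baselines of 0.8 for both enzymes and a normal baseline bilirubin.

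- Protocol AESI: AST 4 ≥ 3, so yes.
- SAP separate rows: ALT > 2, AST > 2, AST > 3 and bilirubin > 2 are all met.
- SAP Hy's law listing: ALT 2.5 is not > 3, so no. The combined PCSV row fails for the same reason.
- eDISH: the patient is plotted, but on the low-ALT side of the line at 3, outside the Hy's law quadrant.

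**2. Hepatic AESI by transaminase.** Table 6 cites PCSVs without naming a step. Single-enzyme examples:

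| Baseline to value | Protocol test | Protocol AESI | SAP steps met |
|---|---|---|---|
| 1.2 to 2.6 | 2.6 ≥ 2 × 1.2 = 2.4 | yes | > 2 only |
| 0.8 to 3.0 | 3.0 ≥ 3 | yes | > 2 only |
| 1.0 to 2.0 | 2.0 ≥ 2 × 1.0 = 2.0 | yes | none |
| 1.8 to 3.2 | 3.2 < 2 × 1.8 = 3.6 | no | > 2 and > 3 |
| 0.8 to 2.2 | 2.2 < 3 | no | > 2 only |

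The rules were then compared on a grid in steps of 0.05, with baseline up to 3 (the entry limit) and value up to 30. Of 31,640 protocol-positive points, the SAP steps taken together miss one, the exact boundary 1.0 to 2.0. They also flag 1,561 protocol-negative points. If only the > 3 step counts, 140 protocol-positive points are lost and 900 protocol-negative points are flagged. These counts show where the rules differ. They are not patient rates.

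**3. Allergic case.** Take an infusion-site urticaria that the investigator judges allergic, starts 3 hours after the infusion and needs treatment.

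- Protocol 10.1.4: an AESI, because treatment was required.
- SAP allergic row: infusion site urticaria is one of the nine excluded terms, so no.
- Infusion-reaction row: Protocol 10.2.4 stops at 2 hours after the infusion, so no.
- All-TEAE tables (SAP 5.8.1): yes.

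**4. Weight of one patient.** 1/14 = 7.1% of Part B. Planned total 6 + 14 = 20, and 1/20 = 5.0%.

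**The case against.** The strongest reply is that little is lost. Appendix 10.4 gives AST the same steps as ALT and adds bilirubin rows. Table 6 makes PCSVs part of the hepatic AESI, and SAP 5.8.3 lists every patient who meets one. A reader might infer that the AST-driven child is absent from the tables, but these rows show otherwise. What is missing is the joint identification. For transaminases the SAP is mostly broader than the protocol, so a reading that many liver AESIs would be dropped also fails unless a single step is used.

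A reader might also infer that the SAP ignores investigators' reports. It does not. The queries run on coded events that investigators entered, Protocol 10.1.3 requires an AESI narrative on the AE form, and all TEAEs are tabulated. Only the AESI designation is left out of these three rows.

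Nor do the documents support calling the neurocognitive list unfit for children. The SAP credits a regulator's request, Table 7's title attributes it to the FDA, and it contains attention and general cognitive terms. No document defines learning or developmental problems as neurocognitive AESIs.

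Two further objections have weight. The protocol writes out no enzyme criteria for Hy's law, so treating AST as a trigger is an inference from its pairing of the two enzymes elsewhere. The allergic gap needs a site-coded term, late onset and treatment or consultation together, and the SAP gives a reason for its exclusions: they are linked to local reactions. That reason does not reconcile the row with the protocol, which has no site exclusion.

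**Conclusion.** The point holds as a mismatch between protocol-defined and SAP-derived AESIs, in three specific places. First, an AST-led rise with raised bilirubin is never labelled a possible Hy's law case, although its components are flagged separately. Second, the hepatic AESI count depends on an unstated choice of step, and neither all steps together nor > 3 x ULN alone matches the protocol. Third, a late, treated, site-coded allergic reaction falls outside both relevant AESI rows while remaining in the TEAE tables.

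Each affected patient shifts a Part B row by 7.1 percentage points, or an all-patient row by 5.0. The documents give no event rate, so the number affected cannot be estimated. The conclusion assumes the Amendment 2 patient numbers, that AST is meant to count equally with ALT as in 10.1.4, and that Table 6 is applied as written. It concerns how safety results are classified and does not touch the efficacy analysis. It is worth settling before database lock.

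**What to change.** - SAP 5.8.3 and 10.4: let ALT or AST above 3 x ULN, with bilirubin above 2 x ULN, trigger the Hy's law listing and the combined PCSV row. Show AST in the eDISH display, for example as a second panel. If ALT alone is intended, say why. This changes the outputs only and leaves the protocol's discontinuation rule as it is.
- SAP Table 6: add a hepatic AESI row that applies the protocol's baseline-dependent rule to ALT and AST. Keep the PCSV steps as a separate laboratory summary.
- SAP 4.8.1.2, 5.8.2 and Table 6: tabulate events reported as AESIs under Protocol 10.1.4 beside the query-based versions, including site-coded allergic events that needed treatment or consultation.
- Correct Table 6's pointer for the neurocognitive terms, which names Table 5; the list is Table 7.

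The cost is SAP text and a little programming, and AESI counts will change slightly. ALT, AST, bilirubin and AE data are already collected. Since Table 6 shows no tick box for these three categories, the AESI designation may have to be taken from the expedited reports rather than the AE page. The documents do not settle that.

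### The SAP rules out pre-existing diabetes for the new-onset diabetes AESI by recorded history alone; the protocol also uses baseline fasting glucose and HbA1c

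*SAP*

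**What the plan says.** Protocol 10.1.4 lists the event as "New onset of diabetes (NOD) in patients without diabetes at baseline". A note there gives three ways in which diabetes can be present at baseline: "Diabetes at baseline is based on documented medical history, baseline fasting glucose" of at least 126 mg/dL, or baseline HbA1c of at least 6.5%. Its laboratory rule for HbA1c is "At least 2 HbA1c measurements" of 6.5% or more in the TEAE period, with one exception, which begins "For patients with only a single measurement available during the TEAE period, a single value". For fasting glucose it also asks for two values and states that a raised last value alone does not qualify (the sentence beginning "For patients with several fasting glucose measurements but with only the last one").

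SAP Appendix 10.3, Table 6, opens its definition with "No medical history of diabetes as specified in" one named CRF page, on cardiovascular history and risk factors. That condition governs all four routes that follow: HbA1c, fasting glucose, a MedDRA high-level term, and a new glucose-lowering medication. No baseline laboratory condition appears. On HbA1c the table repeats the two-value rule and the single-measurement exception, then adds a second exception, "For patients with several HbA1c measurements but only with the last one" at or above 6.5%; that value "will be considered and qualify the patient as NOD by default". For fasting glucose it agrees with the protocol.

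**The concern.** An event labelled new onset should not include disease that was there before the first dose. The protocol prevents this with its baseline laboratory clause, and the SAP omits that clause. The child at issue has no recorded history of diabetes, a day 1 HbA1c of 6.5% or more, and raised values on study. The protocol calls this child diabetic at baseline; the SAP calls the child a new case on evinacumab.

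The added last-value exception is a smaller matter. It changes the confirmation rule for HbA1c without saying so. It can also make a count unstable: under SAP 7.4 the TEAE period of an ongoing patient stops at the data cut-off, so a case resting on the last value at the second-step analysis can disappear when a later normal value arrives.

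Sites report this event to the sponsor within 24 hours under the protocol's wording, while Table 6 has no tick box for it and derives it from data. The reported and tabulated counts can therefore differ.

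**Working it through.** The plan gives no figure on this point, so there is none to reproduce. The check has three parts.

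**1. Can the child reach the table?**
- Protocol 7.2.2, exclusion 6, bars only diabetes diagnosed in the previous 3 months or poorly controlled diabetes (HbA1c above 9%). An unrecognised HbA1c between 6.5% and 9% is not barred.
- In the protocol's Tables 1 and 2, medical history is taken at screening, and HbA1c is first drawn at the day 1 dosing visit. The screening history cannot reflect that result.
- The PCSV limit for HbA1c in SAP 10.4 is above 8%, and SAP 5.9 splits HbA1c by recorded diabetic history. Neither separates out a baseline value of 6.5% to 8% with no history.

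**2. Where do the HbA1c rules disagree?** Take a patient with no recorded history, a baseline HbA1c that is raised or not, and k values in the TEAE period, each raised or not. There are 2 × 2^k patterns.
- Protocol: a case only if baseline is not raised and either at least two values are raised or, when k = 1, that one value is raised.
- SAP: a case if at least two values are raised, or only the last is raised, or, when k = 1, that one value is raised. Baseline is not consulted.

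For k of 2 or more, patterns with at least two raised values number 2^k − 1 − k, and there is one last-only pattern. With a raised baseline the SAP therefore counts (2^k − 1 − k) + 1 = 2^k − k patterns, and the protocol none. With a normal baseline the rules differ only on the last-only pattern.

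| k | Patterns | Disagree, baseline raised | Disagree, baseline normal | Total |
|---|---|---|---|---|
| 1 | 4 | 1 | 0 | 1 |
| 2 | 8 | 4 − 2 = 2 | 1 | 3 |
| 3 | 16 | 8 − 3 = 5 | 1 | 6 |

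In every disagreement the SAP counts a case and the protocol does not. At k = 3, restoring the baseline condition alone removes 5 of the 6. Deleting the last-value sentence alone removes 2 of the 6: the last-only pattern under each baseline. Doing both removes all of them. These are counts of patterns, not probabilities.

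**3. Which k applies where?**
- *Part B, entering Part C on the week 24 visit day.* HbA1c is scheduled at weeks 12 and 24. SAP 4.8.1 ends the Part B TEAE period the day before the first Part C dose, so week 24 falls outside it and k = 1. The last-value sentence then does nothing; the baseline gap still acts.
- *Part B, not entering Part C.* Weeks 12, 24 and 44 are scheduled. The last dose on day 141 plus 168 days is day 309, the target day of the week 44 visit, so k is 2 or 3 and both differences act.
- *Part C and the pooled period.* HbA1c is scheduled at Part C weeks 12, 24, 36 and 48 and twice in follow-up, so both differences act.

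**Size of one case.** 1/14 = 7.1% of Part B; 1/20 = 5% of the planned 6 + 14 patients.

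**The case against.** The strongest reply concerns the last-value sentence. It looks deliberate: Table 6 treats the last value in near-parallel sentences for the two tests, counting it for HbA1c and not for glucose. A high final HbA1c has no later sample to confirm it, and the protocol already accepts an unconfirmed value when it is the only one. The sentence also fits the SAP's other cautious conventions in 6.3, where missing severity becomes severe and missing causality becomes related. This largely stands. A reader might infer that the sentence is a plain error, or that unconfirmed cases enter only through the SAP. The documents do not support either reading: the SAP widens a route that the protocol already has. What remains is that the protocol's two-value rule has one exception, this is not it, and no reason is given.

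On the baseline gap, it can be said that glucose is in the screening chemistry, so diabetes diagnosed from that result would fall under exclusion 6. Protocol 10.1.1 sends abnormal laboratory values at consent to medical history, and 10.1.2 sends other pre-dose events there. These provisions narrow the gap. They do not close it, because HbA1c is first seen on day 1 and Table 6 looks at one named CRF page.

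It can also be said that 10.1.4 is a reporting section, that SAP 1.2.4 claims only to reflect the protocol's statistical section, and that other AESIs are also defined more broadly in the SAP. All true. But 10.1.4 holds the protocol's only definition of this event, and it refers to the TEAE period. Version lag is not an evident explanation: the amendment history places the event's addition in Amendment 1, which the SAP says it follows, and Amendment 2 does not name 10.1.4 among its changed sections.

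Finally, HbA1c change from baseline is summarised (SAP 4.9 and 5.9), so a raised baseline would not be wholly hidden. That lessens the consequence but does not correct the AESI count.

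**Conclusion.** The baseline gap holds. As written, Table 6 can present diabetes that preceded treatment as new onset, in every analysis period that has an on-study HbA1c or glucose value. Caution in safety reporting does not justify this, since such a case is not new under the protocol's definition.

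The last-value sentence is a secondary, undeclared departure to be reconciled. It matters mainly for patients who do not enter Part C, for Part C itself and for the pooled period. A reader might infer that it distorts Part B generally. For patients who start Part C on the week 24 visit day it has no effect in the Part B TEAE period.

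A reader might also take 7.1% as an estimate of misclassification. It is one patient over 14 and would apply to any event in Part B. The documents give no rate of raised HbA1c in these children, so how often a case would be added cannot be derived from them.

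The effect is limited to one descriptive AESI count, which is assumed to be rare. No testing depends on it and the primary endpoint is not affected. The conclusion rests on reading the protocol's two-value rule as exhaustive apart from its stated exception, and on Table 6 being programmed as written.

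**What to change.** In SAP Table 6, replace the history-only condition with the protocol's three criteria for diabetes at baseline: documented history, baseline fasting glucose of at least 126 mg/dL, or baseline HbA1c of at least 6.5%. Apply it to all four routes.

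Reconcile the last-value HbA1c sentence with Protocol 10.1.4. One way is to tabulate new-onset diabetes under the protocol's two-value rule and list single-last-value cases separately, which keeps the sensitivity that the sentence appears to seek. If the sponsor prefers to keep it in the main count, the SAP should state the departure and the reason.

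The cost is one line of SAP text for the baseline condition, a sentence or a listing for the second point, and a few lines of code. No new data are needed: baseline HbA1c and chemistry, including glucose, are already scheduled.
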